4.5.12 Samples for Roche Clinical Repository

4.5.12.1 Overview of the Roche Clinical Repository

The Roche Clinical Repository (RCR) is a centrally administered group of facilities used for the long-term storage of human biologic specimens, including body fluids, solid tissues, and derivatives thereof (e.g., DNA, RNA, proteins, and peptides). The collection and analysis of RCR specimens will facilitate the rational design of new pharmaceutical agents and the development of diagnostic tests, which may allow for individualized drug therapy for patients in the future.

Specimens for the RCR will be collected from patients who give specific consent to participate in this optional research. RCR specimens will be used to achieve the following objectives:

- To study the association of biomarkers with efficacy, adverse events, or disease progression
- To increase knowledge and understanding of disease biology
- To study drug response, including drug effects and the processes of drug absorption and disposition
- To develop biomarker or diagnostic assays and establish the performance characteristics of these assays

4.5.12.2 Approval by the Institutional Review Board or Ethics Committee

Collection and submission of biological samples to the RCR is contingent upon the review and approval of the exploratory research and the RCR portion of the Informed Consent Form by each site's Institutional Review Board or Ethics Committee (IRB/EC) and, if applicable, an appropriate regulatory body. If a site has not been granted approval for RCR sampling, this section of the protocol (see Section 4.5.10) will not be applicable at that site.

4.5.12.3 Sample Collection

The following samples may be collected for patients who have signed the RCR optional consent:

- Optional freshly collected biopsy samples during the study (preferably at disease progression, if clinically feasible)
- Remaining fluids (urine, plasma, and whole blood derivatives) after study-related tests have been performed
- Remaining FFPE tissue (with the exception of archival FFPE blocks, which will be returned to sites) after study-related tests have been performed.

For all samples, dates of consent and specimen collection should be recorded on the associated RCR page of the eCRF. For sampling procedures, storage conditions, and shipment instructions, see the laboratory manual.

RCR specimens will be destroyed no later than 15 years after the date of final closure of the associated clinical database. The RCR storage period will be in accordance with the IRB/EC-approved Informed Consent Form and applicable laws (e.g., health authority requirements).

4.5.12.4 Confidentiality Confidentiality for All RCR Specimens

Specimens and associated data will be labeled with a unique patient identification number.

Patient medical information associated with RCR specimens is confidential and may be disclosed to third parties only as permitted by the Informed Consent Form (or separate authorization for use and disclosure of personal health information) signed by the patient, unless permitted or required by law.

Data generated from RCR specimens must be available for inspection upon request by representatives of national and local health authorities, and Roche monitors, representatives, and collaborators, as appropriate.

Data derived from RCR specimen analysis on individual patients will generally not be provided to study investigators unless a request for research use is granted. The aggregate results of any research conducted using RCR specimens will be available in accordance with the effective Roche policy on study data publication.

Any inventions and resulting patents, improvements, and/or know-how originating from the use of the RCR data will become and remain the exclusive and unburdened property of Roche, except where agreed otherwise.

Additional Confidentiality for Specimens Used for Genetic Research

Given the sensitive nature of genetic data, Roche has implemented additional processes to ensure patient confidentiality for RCR specimens collected for genetic research. Upon receipt by the RCR, specimens for genetic research are "double-coded" by replacing the patient identification number with a new independent number. Data generated from the use of these specimens and all clinical data transferred from the clinical database and considered relevant are also labeled with this same independent number. A "linking key" between the patient identification number and this new independent number is stored in a secure database system. Access to the linking key is restricted to authorized individuals and is monitored by audit trail. Legitimate operational reasons for accessing the linking key are documented in a standard operating procedure.

Access to the linking key for any other reason requires written approval from the Pharma Repository Governance Committee and Roche's Legal Department, as applicable.

4.5.12.5 Consent to Participate in the Roche Clinical Repository

The Informed Consent Form will contain a separate section that addresses participation in the RCR. The investigator or authorized designee will explain to each patient the objectives, methods, and potential hazards of participation in the RCR. Patients will be told that they are free to refuse to participate and may withdraw their specimens at any time and for any reason during the storage period. A separate, specific signature will be required to document a patient's agreement to provide optional RCR specimens. Patients who decline to participate will not provide a separate signature.

The investigator should document whether or not the patient has given consent to participate by completing the RCR Research Sample Informed Consent eCRF.

In the event of an RCR participant's death or loss of competence, the participant's specimens and data will continue to be used as part of the RCR research.

4.5.12.6 Withdrawal from the Roche Clinical Repository

Patients who give consent to provide RCR specimens have the right to withdraw their specimens from the RCR at any time for any reason. *After withdrawal of consent, any remaining samples will be destroyed or will no longer be linked to the patient.* If a patient wishes to withdraw consent to the testing of his or her specimens, the investigator must inform the Medical Monitor in writing of the patient's wishes through use of the RCR Subject Withdrawal Form and, if the study is ongoing, must enter the date of withdrawal on the RCR Research Sample Withdrawal of Informed Consent eCRF. The patient will be provided with instructions on how to withdraw consent after the study is closed. A patient's withdrawal from Study WO29635 does not, by itself, constitute withdrawal of specimens from the RCR. Likewise, a patient's withdrawal from the RCR does not constitute withdrawal from Study WO29635.

If a patient wishes to withdraw consent to the testing of his or her specimens after closure of the site, the investigator must inform the Sponsor by emailing the study number and patient number to the following email address:

[contact]

4.6 PATIENT, TREATMENT, STUDY, AND SITE DISCONTINUATION

4.6.1 Patient Discontinuation

Patients have the right to voluntarily withdraw from the study at any time for any reason. In addition, the investigator has the right to withdraw a patient from the study at any time. Reasons for withdrawal from the study may include but are not limited to the following:

- Patient withdrawal of consent at any time

- Any medical condition that the investigator or Sponsor determines may jeopardize the patient's safety if he or she continues in the study
- Investigator or Sponsor determines it is in the best interest of the patient
- Patient non-compliance

Every effort should be made to obtain information on patients who withdraw from the study. The primary reason for withdrawal from the study should be documented on the appropriate eCRF. However, patients will not be followed for any reason after consent has been withdrawn. Patients who withdraw from the study will not be replaced.

4.6.2 Study Treatment Discontinuation

Patients must discontinue study treatment if they experience any of the following:

- Persistence/recurrence of disease with high grade lesion (any pT1, high-grade Ta, or CIS) detected any time on or after the 6-month bladder biopsy.
 - Patients with persistent and/or recurrent high-grade NMIBC without progression at 12 weeks may continue in the study, provided there is no evidence of progression to muscle-invasive disease.
- Disease progression (e.g., muscle-invasive or metastatic UC)
- Symptomatic deterioration (i.e., uncontrollable pain secondary to disease or unmanageable ascites, etc.) attributed to disease progression as determined by the investigator after integrated assessment of radiographic data, biopsy results, and clinical status.
- Intolerable toxicity related to atezolizumab or the combination of BCG and atezolizumab, including development of an immune-mediated adverse event determined by the investigator to be unacceptable given the individual patient's potential response to therapy and severity of the event
- Any medical condition that may jeopardize the patient's safety if he or she continues on study treatment
- Use of another non-protocol anti-cancer therapy (see Section [4.4.2](#))
- Pregnancy

The primary reason for study treatment discontinuation must be documented in the eCRF.

4.6.3 Study and Site Discontinuation

The Sponsor has the right to terminate this study at any time. Reasons for terminating the study may include but are not limited to the following:

- The incidence or severity of adverse events in this or other studies indicates a potential health hazard to patients.
- Patient enrollment is unsatisfactory.

The Sponsor will notify the investigator if the Sponsor decides to discontinue the study.

The Sponsor has the right to close a site at any time. Reasons for closing a site may include but are not limited to the following:

- Excessively slow recruitment
- Poor protocol adherence
- Inaccurate or incomplete data recording
- Non-compliance with the International Conference on Harmonisation Guideline for Good Clinical Practice
- No study activity (i.e., all patients have completed and all obligations have been fulfilled)

5. ASSESSMENT OF SAFETY

5.1 SAFETY PLAN

Measures will be taken to ensure the safety of patients participating in this study, including the use of inclusion and exclusion criteria (see Section 4.1.1 and Section 4.1.2) and close monitoring (as indicated below and in Section 4.5).

An iDMC has also been incorporated into the study design to periodically review aggregate safety and efficacy data (please refer to the iDMC Charter for a detailed monitoring plan).

BCG is an approved treatment for patients with NMIBC. Additional information on the risks and precautions associated with BCG therapy are provided in the OncoTICE prescribing information.

Eligibility

Eligibility criteria were selected to guard the safety of patients in this study. Results from the nonclinical toxicology studies with atezolizumab, as well as the nonclinical/clinical data from other PD-L1/PD-1 inhibitors, were taken into account. Specifically, patients at risk for study-emergent autoimmune conditions or with a prior diagnosis of autoimmune disease, patients with evidence of acute infections, and patients who have received a live-attenuated viral vaccine within 28 days before Day 1 are excluded from the study (see Section 4.1.2).

Monitoring

Safety will be evaluated in this study through the monitoring of all serious adverse events, defined and graded according to NCI CTCAE v4.0. General safety assessments will include serial interval histories, physical examinations, and specific laboratory studies, including serum chemistries and blood counts (see Appendix 1 and Appendix 2 for the list and timing of study assessments). Laboratory values must be reviewed prior to each infusion.

During the study, patients will be closely monitored for the development of any signs or symptoms of autoimmune conditions and infection. All serious adverse events and protocol-defined events of special interest (see Sections 5.2.2 and 5.2.3) will be reported in an expedited fashion (see Section 5.4.2). In addition, the Medical Monitor will review and evaluate observed adverse events on a regular basis. An iDMC will review safety and efficacy data as described in the Section 3.2.

Patients who experience a serious adverse event or protocol defined events of special interest will be followed for safety for 90 days following their last dose of study drug or until they receive another anti-cancer therapy, whichever comes first. Patients who experience all other adverse events will be followed for safety for 30 days following their last dose of study drug or until they receive another anti-cancer therapy, whichever comes first.

Patients who have an ongoing study treatment-related adverse event upon study completion or at discontinuation from the study will be followed until the event has resolved to baseline grade, the event is assessed by the investigator as stable, new anti-cancer treatment is initiated, the patient is lost to follow-up, the patient withdraws consent, or it has been determined that study treatment or participation is not the cause of the adverse event.

The potential safety issues anticipated in this study, as well as measures intended to avoid or minimize such toxicities, are outlined in the following sections. Refer to the Atezolizumab Investigator's Brochure for a complete summary of safety information.

5.1.1 Risks Associated with Atezolizumab

Atezolizumab has been associated with risks such as the following: IRRs and *immune-mediated* hepatitis, pneumonitis, colitis, pancreatitis, diabetes mellitus, hypothyroidism, hyperthyroidism, adrenal insufficiency, hypophysitis, Guillain-Barré syndrome, myasthenic syndrome or myasthenia gravis, meningoencephalitis, myocarditis, nephritis, and myositis. *Immune-mediated reactions may involve any organ system and may lead to hemophagocytic lymphohistiocytosis and macrophage activation syndrome (considered to be potential risks for atezolizumab).* Refer to [Appendix 12](#) of the protocol and Section 6 of the Atezolizumab Investigator's Brochure for a detailed description of anticipated safety risks for atezolizumab.

5.1.2 Risks Associated with BCG

Although intravesical BCG is generally well tolerated, the potential for adverse effects and severe complications exists with prolonged therapy and include local and systemic infectious complications. Adverse events commonly seen with BCG treatment include but are not limited to the following: urinary tract infection, anorexia, unclassified cardiac disorders, nausea/vomiting, diarrhea, liver involvement, skin rash, arthralgia/myalgia/arthritis, dysuria, hematuria, urinary frequency, urinary urgency, BCG cystitis, bladder cramps/pain, urinary incontinence, contracted bladder, fever, malaise,

and chills (Lamm et al. 1991). Additional complications include clinical granulomatous prostatitis, pneumonitis, hepatitis, ureteral obstruction, epididymitis, renal abscess, sepsis, arthritis, osteomyelitis, and cytopenias (Brausi et al. 2014).

The proper administration of BCG is essential for avoiding intravascular dissemination of the bacillus.

The following is a summary of AUA guidelines for avoiding BCG transmission to others after BCG exposure:

To avoid transmission of BCG to others, for 6 hours after treatment, patients should void (urinate) while seated to avoid splashing of urine. Urine voided during this time should be disinfected with 2 cups of household bleach in the toilet water and allowing it to stand for 15–2 minutes before flushing.

Men receiving BCG treatment can pass on BCG during sex. To protect their partner from coming into contact with BCG, men should not have sex for 48 hours after each treatment. Men should use condoms while taking BCG and for six weeks after treatment has ended.

Both men and women should not conceive a child (get pregnant) while taking BCG treatments. Barrier methods of contraception, such as condoms, are recommended while taking BCG. Men and women should discuss with their doctor when it is safe to conceive a child after therapy.

Women should not breastfeed while taking this medication.

5.1.2.1 Constitutional Symptoms (Flu-like Symptoms)

Flu-like symptoms (malaise, fever and chills) may occur with both BCG treatment and atezolizumab. In patients who develop flu-like symptoms, disseminated BCG infection should be evaluated and ruled out before attributing to atezolizumab. The management of disseminated BCG infection requires the administration of antibiotics and steroids would be contraindicated. Patients should be monitored for the presence of symptoms and signs of toxicity after each intravesical treatment. Flu-like symptom attributable to BCG may be managed per the OncoTICE prescribing information.

Additional guidelines for management of patients who develop flu-like symptoms are provided in [Table 8](#).

5.1.2.2 Local Bladder Symptoms

Symptoms of bladder irritability (i.e., bladder pain, bladder spasm), related to the inflammatory response induced, are reported in approximately 60% of patients receiving BCG (Brausi et al. 2014). The symptoms typically begin 4–6 hours after instillation and last 24–72 hours.

Grade ≥ 3 dysuria occurs in 11% of patients and usually seen after the third instillation and tends to increase in severity with each subsequent administration. The mechanism of action has not been firmly established, but is most consistent with an immunological mechanism. There is no evidence that dose reduction or anti-tuberculous drug therapy can prevent or lessen the irritative toxicity of BCG.

Guidelines for management of patients who develop local bladder symptoms are provided in [Table 8](#).

5.1.3 Management of Patients Who Experience Specific Adverse Events

There will be no dose reduction for atezolizumab in this study. Patients may temporarily suspend atezolizumab for up to 12 weeks beyond last dose if they experience adverse events that require a dose to be withheld. If atezolizumab is withheld because of related adverse events for > 12 weeks beyond the last dose, then the patient will be discontinued from atezolizumab and will be followed for safety and efficacy as specified in Section 5.5. If, in the judgment of the investigator, the patient is likely to derive clinical benefit from resuming atezolizumab after a hold > 12 weeks, atezolizumab may be restarted with the approval of the Medical Monitor.

If a patient must be tapered off steroids used to treat adverse events, atezolizumab may be withheld for an additional time beyond 12 weeks from the last dose until steroids are discontinued or reduced to prednisone dose (or dose equivalent) ≤ 10 mg/day. The acceptable length of interruption will depend on agreement between the investigator and the Medical Monitor.

Note, if systemic corticosteroids must be initiated in patients receiving weekly BCG installations, either during BCG induction or any BCG maintenance course, BCG must be withheld throughout the duration of systemic corticosteroid therapy to minimize the risk of systemic BCG infection. BCG instillations should not be resumed until the patient has discontinued systemic corticosteroids.

Dose interruptions for reason(s) other than toxicity, such as surgical procedures, may be allowed with Medical Monitor approval. The acceptable length of interruption will depend on agreement between the investigator and the Medical Monitor.

Guidelines for the management of fever, local bladder symptoms, and influenza-like illness are presented in [Table 8](#), as these events may result from or be potentiated by the combination of BCG and atezolizumab. Refer to [Appendix 12](#) for additional management guidelines for immune-mediated adverse events.

See Section 4.3.2.1 for guidelines for the management of infusion-related reactions and [Appendix 8](#) for precautions for anaphylaxis.

Table 8 Guidelines for Management of Specific Adverse Events

Severity	Management
Influenza-like illness	
Arthralgia/chills	
Grade ≤ 2	
 Continue atezolizumab. Treat symptoms with non-steroidal anti-inflammatory drugs (e.g., ibuprofen).
Grade 3/4	
 Withhold atezolizumab. Consider starting 10 mg/day oral prednisone or equivalent, with taper over 1–2 weeks. Resume atezolizumab if symptoms resolve and corticosteroid dose is equivalent to 10 mg/day. Refer to the TICE prescribing information for additional management guidelines pertaining to BCG.
Fever	
< 101° F (38.3° C)	
 Continue atezolizumab and BCG (patients receiving induction or maintenance BCG at time of symptom) Treat symptoms with non-steroidal anti-inflammatory drugs (e.g., ibuprofen). Withhold BCG and atezolizumab.
$\geq 101^{\circ}$ F (38.3° C)	
 For fever < 24 hours, and in absence of other new grade ≥ 2 symptoms, evaluate and rule out co-existing infection including urine and blood culture, blood tests, and chest X-ray. Consider consultation with infectious disease specialist. For fever > 24hours, would recommend immediate consultation with infectious disease specialist, discontinuation of BCG instillations, urine and blood culture, blood tests, and chest X-ray. Consider initiation of ≥ 2 antimicrobial agents including coverage with anti-tuberculosis therapy while diagnostic evaluation is being conducted. Refer to the TICE prescribing information for additional management guidelines pertaining to BCG.
Local bladder symptoms	
Dysuria	
 Refer to the TICE prescribing information for management guidelines pertaining to BCG.
Frequency	
 Refer to the TICE prescribing information for management guidelines pertaining to BCG.
Hematuria	
 Refer to the TICE prescribing information for management guidelines pertaining to BCG.
Local inflammation (e.g., epididymitis, prostatitis, orchitis)	
 Refer to the TICE prescribing information for management guidelines pertaining to BCG.

BCG = bacille Calmette-Guérin; GGO = ground-glass opacity; IV = intravenous; LFT = liver function test; TNF- α = tumor necrosis factor- α ; TSH = thyroid-stimulating hormone; ULN = upper limit of normal.

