Patients with right upper-quadrant abdominal pain and/or unexplained nausea or vomiting should have liver function tests (LFTs) performed immediately and reviewed before administration of the next dose of study drug.

For patients with elevated LFTs, concurrent medication, viral hepatitis, and toxic or neoplastic etiologies should be considered and addressed, as appropriate.

Table 2 Management Guidelines for Hepatic Events

Event	Management
Hepatic event, Grade 1	
 • Continue atezolizumab. • Monitor LFTs until values resolve to within normal limits.
Hepatic event, Grade 2	
All events:
 
 • Monitor LFTs more frequently until return to baseline values. 
Events of > 5 days' duration:
 
 • Withhold atezolizumab for up to 12 weeks after event onset. ^a • Initiate treatment with 1–2 mg/kg/day oral prednisone or equivalent. • If event resolves to Grade 1 or better, resume atezolizumab. ^b • If event does not resolve to Grade 1 or better while withholding atezolizumab, permanently discontinue atezolizumab and contact Medical Monitor. ^c

LFT=liver function test.

^a Atezolizumab may be withheld for a longer period of time (i.e., > 12 weeks after event onset) to allow for corticosteroids (if initiated) to be reduced to ≤ 10 mg/day oral prednisone or equivalent. The acceptable length of the extended period of time must be agreed upon by the investigator and the Medical Monitor.

^b If corticosteroids have been initiated, they must be tapered over ≥ 1 month to ≤ 10 mg/day oral prednisone or equivalent before atezolizumab can be resumed.

^c Resumption of atezolizumab may be considered in patients who are deriving benefit and have fully recovered from the *immune-mediated* event. Patients can be re-challenged with atezolizumab only after approval has been documented by both the investigator (or an appropriate delegate) and the Medical Monitor.

Appendix 12

Risks Associated with Atezolizumab and Guidelines for Management of Adverse Events Associated with Atezolizumab (cont.)

Table 2 Management Guidelines for Hepatic Events (cont.)

Event	Management

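### Table 8 offers prednisone for Grade 3/4 flu-like symptoms without carrying or citing the BCG-infection and BCG-hold safeguards in Sections 5.1.2.1 and 5.1.3

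*Combined protocol and SAP*

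**What the plan says.** Section 5.1.2.1 deals with flu-like symptoms, which it lists as malaise, fever and chills and says either drug can cause. It states: "In patients who develop flu-like symptoms, disseminated BCG infection should be evaluated and ruled out before attributing to atezolizumab". The next sentence reads: "The management of disseminated BCG infection requires the administration of antibiotics and steroids would be contraindicated". The section then refers sites to Table 8 for further guidance.

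Section 5.1.3, in the text before Table 8, says that if systemic corticosteroids are started in a patient on weekly instillations, "BCG must be withheld throughout the duration of systemic corticosteroid therapy to minimize the risk of systemic BCG infection". BCG is not to restart until the steroid has been stopped. The same section explains that Table 8 covers fever, bladder symptoms and influenza-like illness because the combination may cause or worsen them.

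In Table 8, the influenza-like illness row for Grade 3/4 arthralgia or chills has four instructions:
- hold atezolizumab;
- "Consider starting 10 mg/day oral prednisone or equivalent, with taper over" 1–2 weeks;
- restart atezolizumab if symptoms resolve and the steroid dose is equivalent to 10 mg/day;
- "Refer to the TICE prescribing information for additional management guidelines pertaining to BCG".

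The fever rows are separate. Below 101 °F both drugs continue and symptoms are treated. At 101 °F or above both drugs are held and an infection work-up is described.

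**The concern.** Table 8 is what a site is likely to have open when a patient on the combination reports severe chills. For that presentation it moves from holding atezolizumab to considering a steroid, in the setting where the body text warns that the cause may be a live-organism infection in which steroids are contraindicated. A reader of the row alone sees no prompt to exclude that infection and no instruction to hold BCG. Systemic BCG infection is not a remote matter in this protocol: Section 4.3.1.2 describes the product as a live attenuated culture, and Section 5.2.3 lists BCG infection as an adverse event of special interest. At stake is whether the guidance used at the point of care agrees with the safeguards the protocol itself states.

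**Working it through.** No formula applies to the main point. The check is to set the passages side by side.

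| Element | Sections 5.1.2.1 and 5.1.3 | Flu-like row, Grade 3/4 | Fever row, below 101 °F | Fever row, 101 °F or above |
|---|---|---|---|---|
| Exclude infection | Yes, before attribution to atezolizumab | Absent | Absent | Present |
| Steroid contraindicated in disseminated BCG infection | Stated | Absent | Absent | Absent |
| BCG during systemic steroid | Must be held | Not stated; pointer to TICE prescribing information | Says continue BCG (silent on steroid) | BCG held because of fever |
| Reference back to 5.1.2.1 or 5.1.3 | Not applicable | None | None | None |

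One assumption is needed. In the extracted text, the line holding both drugs is printed at the end of the lower-temperature cell, next to an instruction to continue both. I read it as the first instruction of the higher-temperature row, which is the only reading that makes sense of both.

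Now follow a patient with Grade 3/4 chills through the table.

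1. Temperature 101 °F or above: both rows apply, and the fever row supplies the infection work-up and the BCG hold.
2. Temperature below 101 °F, or no fever: the flu-like row applies. Steroid may be considered, and nothing in the table leads to an infection work-up.
3. Fever below 101 °F and steroid started: the fever row says continue BCG and 5.1.3 says hold it. These two instructions cannot both be followed.

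The overlap in subject matter is direct for chills, which appear in both 5.1.2.1 and the row. It is less direct for arthralgia, which is in the row but not in the 5.1.2.1 list.

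Maximum exposure, from the planned enrolment in Section 3.1.1:
- Combination patients: 18 (Cohort 1B, upper end) + 10 (Cohort 1 expansion, if all go to 1B) + 10 (Cohort 2) + 10 (Cohort 3) + 10 (Cohorts 2 and 3 expansion) = 58. With 12 in Cohort 1A the total is 58 + 12 = 70, matching the plan.
- Instillations per patient: 6 (induction) + 5 courses × 3 = 21. Maintenance Courses 2–5 are optional in Cohort 1B, so the non-optional number there is 6 + 3 = 9.

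Both are ceilings on exposure. The row concerns only patients who develop Grade 3/4 arthralgia or chills. The documents give no rate for that on the combination and none for disseminated BCG infection.

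**The case against.** The strongest reply is that the safeguards are already in the protocol. Section 5.1.2.1 presents Table 8 as additional guidance, so the table supplements that section and does not replace it. The BCG hold is mandatory and sits in the same section as the table. Sections 4.4.1 and 4.4.2 put systemic corticosteroids behind consultation with the Medical Monitor. Section 4.5 calls for a toxicity assessment before each dose of either drug. The row sends sites to the TICE prescribing information, whose content cannot be checked here. A site that reads all of this would probably act consistently.

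Most of that stands, and it limits the point. It does not remove it: the row cites neither safeguard, and case 3 above is a conflict in the text however carefully it is read.

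Four stronger readings are tempting and are not supported.

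- *The protocol requires infection to be excluded before any steroid.* Section 5.1.2.1 uses should, and ties the exclusion to attribution. Applying it before steroid is an inference, though a close one given the sentence that follows. Table 8 in turn only says consider.
- *Sites would go on instilling BCG under steroid.* That would mean disregarding the explicit hold in 5.1.3.
- *Appendix 12 has the same gap for hepatic events.* There, "concurrent medication, viral hepatitis, and toxic or neoplastic etiologies should be considered and addressed, as appropriate", and concurrent medication or toxic causes can reasonably include BCG. Steroid at Grade 2 is limited to events lasting more than 5 days, and the Grade 3/4 guidance includes considering referral and liver biopsy to find the cause.
- *BCG infection would be under-counted and events wrongly attributed to atezolizumab.* Causality is assessed separately for each drug (Section 5.3.4), and BCG infection must be reported within 24 hours as an event of special interest (Section 5.2.3). Nothing in the documents shows under-counting.

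**Conclusion.** The inconsistency is real and should be corrected. The Grade 3/4 influenza-like illness row permits a steroid without carrying or citing the infection exclusion in 5.1.2.1 or the BCG hold in 5.1.3, and the fever row below 101 °F conflicts with 5.1.3 once a steroid is given. Surrounding text reduces the practical risk, so this is a failure of the table to agree with its own section, not an absence of safeguards from the protocol.

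Its size cannot be stated as an event count. The figures of 58 patients and 21 instillations should not be read as patients or doses affected. The conclusion rests on the reading of the fever rows described above and on the protocol text alone. If the TICE prescribing information covers the infection step, the gap is smaller in practice, but the conflict over continuing BCG remains. No view is taken on which clinical instruction is right.

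**What to change.** Reconcile the Table 8 influenza-like illness and fever rows with Sections 5.1.2.1 and 5.1.3. At a minimum, add an explicit cross-reference in the Grade 3/4 row to both sections for Cohorts 1B, 2 and 3, and resolve how the below-101 °F instruction on BCG stands when a systemic steroid is started. The clinical content is for the sponsor to settle. The cost is a wording change in one table and a letter to sites, with no added visits, assessments or patients.
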